6.4 Study Treatment Compliance

When patients are dosed at the site, study treatment will be administered directly by the Investigator or designee. All dosing by the patient throughout the treatment period will also be documented in the patient's dosing diary. The date and time of each dose administered in the clinic will be recorded in the source documents. The dose of study treatment and study patient identification will be confirmed at the time of dosing by a member of the study site staff other than the person administering the study treatment.

For self-administration of the study treatment at home by the patient, compliance with study treatment will be assessed at each visit. Compliance will be assessed by direct questioning and counting returned tablets during the site visits and documented in the source documents and relevant form. Deviations from the prescribed dosage regimen should be recorded. Final drug accountability will be done by counting returned tablets at the patient's final visit.

A record of the quantity of study treatment dispensed to and administered by each patient must be maintained and reconciled with study treatment and compliance records. Treatment start and stop dates, including dates for treatment delays and/or dose reductions will also be recorded.

6.5 Continued Access to Study Treatment After the End of the Study

The study treatment will not be available to the patients at the end of the study.

Version 3.0 39 of 85 20 April 2022

6.6 Treatment of Overdose

For this study, any dose of study treatment greater than 20 tablets within a 24-hour time period will be considered an overdose.

In the event of an overdose, the Investigator should:

- Contact the medical monitor immediately.
- Evaluate the patient to determine, in consultation with the medical monitor, whether study treatment should be interrupted or whether the dose should be reduced.
- Closely monitor the patient for any AE/SAE and laboratory abnormalities until study treatment can no longer be detected systemically.

6.7 Concomitant Therapy

Any medication or vaccine (including over-the-counter or prescription medicines, recreational drugs, vitamins, and/or herbal supplements) that the patient is receiving at the time of enrollment or receives during the study must be recorded along with:

- reason for use
- dates of administration including start and end dates
- dosage information including dose and frequency

As much as possible, the dose and frequency of all concomitant medications taken for chronic conditions except for diabetes mellitus (see Section 6.7.2) should be held stable during the study. The Medical Monitor should be contacted if there are any questions regarding concomitant or prior therapy.

6.7.1 Prohibited Treatments

The class of drugs prohibited in the study are those that affect GI motility, either positively or negatively, and therefore could confound the assessment of the efficacy of the study treatment on the signs and symptoms of gastroparesis.

Prohibited concomitant treatment includes cannabis, opioids, GLP-1 agonists (e.g. exenatide, liraglutide, semaglutide or dulaglutide, or pramlintide), cisapride, tegaserod, prucalopride, metoclopramide, bethanechol, domperidone and erythromycin or any other medications that are contraindicated for patients with gastroparesis.

Version 3.0 40 of 85 20 April 2022

IMPORTANT: Patients should be instructed to consult with the Investigator before taking any new medication or changing medications and/or dosing regimens throughout the study.

Drugs that are known to be strong inhibitors or inducers of Cytochrome P450 (CYP) (most likely CYP3A4 and CYP1A2) may significantly alter exposure to the investigational product, and as such, are strictly prohibited while on the study. Examples of CYP inhibitors include cimetidine, ciprofloxacin, fluvoxamine, clarithromycin, diltiazem, grapefruit juice, and itraconazole. Examples of CYP inducers include carbamazepine, phenobarbital, tobacco, and St. John's wort.

P-glycoprotein (P-gp), breast cancer resistance protein (BCRP), and gastric acid reducing agents may also significantly alter the exposure of the investigational product and as such, are strictly prohibited while on study. Examples of P-gp inhibitors include cyclosporine, amiodarone, and itraconazole as well as BCRP inhibitors include novobiocin, sulfasalazine and cyclosporine A which may potentially increase the systemic exposure. Examples of P-gp inducers include carbamazepine, phenytoin and rifampin. Examples of BCRP inducers and gastric acid reducing agents include venlafaxine, apalutamide and dovitinib as well as PPIs (esomeprazole, lansoprazole, omeprazole, etc), H2 blockers (ranitidine, famotidine, nizatidine) which may potentially decrease the systemic exposure.

6.7.2 Permitted Treatments

Any medication or vaccine (including over-the-counter or prescription medicines, vitamins, and/or herbal supplements) that the patient is receiving at the time of enrollment or receives during the study must be recorded in the eCRF along with:

- indication
- dates of administration including start and end dates
- dosage information including dose and frequency

Diabetic gastroparesis patients enrolled in the study will likely consist mostly of patients receiving one or more prescription medications for blood-glucose control. Good clinical practice allows for frequent adjustment of medication by patients and their health care providers to minimize large fluctuations in glycemia, and this practice is encouraged in this study.

It should be remembered that certain diabetic drugs (see Section 6.7.1) delay gastric emptying and are prohibited during this study. Other therapy considered necessary for the patient's welfare

Version 3.0 41 of 85 20 April 2022

may be given at the discretion of the Investigator. If the permissibility of a specific medication/treatment is in question, please contact the Medical Monitor.

The Medical Monitor or designee should be contacted if there are any questions regarding concomitant or prior therapy.

6.7.3 Rescue Medicine

Use of medications that may impact efficacy evaluations is strongly discouraged at any time after Visit 1 in the study. However, patients who experience severe symptoms of gastroparesis after entering the Treatment Period may receive a single day of treatment per week with an anti-emetic drug, but should avoid such treatment, if possible, on the day prior to and day of treatment visits. If a patient requires an anti-emetic drug (e.g., 5-HT₃ receptor antagonists, NK1 receptor antagonists) for more than 1 day a week, or requires an antiemetic drug once weekly repeatedly (i.e., more than 2 weeks while on study), the Investigator should contact the Medical Monitor to discuss the safety of the patient continuing in the study.

The following rescue medications may be used:

- ondansetron or promethazine (tablet, syrup or suppositories) for emesis
- loperamide for diarrhea
- Tramadol for pain

The date and time of rescue medication administration as well as the name and dosage regimen of the rescue medication must be recorded.

7 Discontinuation/Withdrawal Criteria

It may be necessary for a patient to permanently discontinue study treatment. Reasons for discontinuation from study treatment and/or the study may include the following:

- Adverse event
- Death
- Failure to meet randomization criteria
- Lack of efficacy
- Lost to follow-up
- Investigator decision
- Pregnancy

Version 3.0 42 of 85 20 April 2022

- Protocol deviation
- Screen failure
- Site terminated by the Sponsor
- Study terminated by the Sponsor
- Withdrawal by the patient

The reason for discontinuation should be clearly documented on the appropriate eCRF. Discontinuation of study treatment also requires discontinuation from the study. If study treatment is permanently discontinued, the patient will not remain in the study. See the SoA (Table 1) for data to be collected at the time of discontinuation of study treatment and follow-up and for any further evaluations that need to be completed.

A patient may withdraw from the study at any time at their own request or may be withdrawn at any time at the discretion of the Investigator for safety, behavioral, or compliance reasons. The patient will be permanently discontinued from the study treatment and the study at that time.

If the patient withdraws consent for disclosure of future information, the Sponsor may retain and continue to use any data collected before such a withdrawal of consent.

If a patient withdraws from the study, he/she may request destruction of any samples taken and not tested, and the Investigator must document this in the site study records.

At the time of discontinuing from the study, if possible, an early discontinuation visit should be conducted, as shown in the SoA (Table 1). Refer to the SoA for data to be collected at the time of study discontinuation and follow-up and for any further evaluations that need to be completed.

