5.2 Exclusion Criteria

Patients are excluded from the study if any of the following criteria apply:

- 1. Has acute, severe gastroenteritis and pronounced dehydration in the past 48 hours prior to Screening, chronic parenteral feeding or persistent severe vomiting.
- 2. Has known hypersensitivity to Spirulina, egg, milk products or wheat allergens.
- 3. Has a known disturbance of small intestinal absorption, exocrine pancreatic function, liver metabolism or pulmonary function.
- 4. Has a history of anorexia nervosa or bulimia.
- 5. Previous history of bezoars (the presence of retained liquid, bile, or small amounts of poorly organized food residue is permitted).
- 6. Prior surgery involving any gastrointestinal surgery, including the luminal gastrointestinal (GI) tract (cholecystectomy and appendectomy are permitted if performed greater than (>) 3 months prior to baseline GEBT).
- 7. Any abdominal or pelvic surgery within the past 3 months.
- 8. Known or history of the following GI conditions: inflammatory bowel disease; irritable bowel syndrome with diarrhea; or any other active disorder that could explain symptoms in the opinion of the investigator.
- 9. Has active diverticulitis, diverticular stricture, and other intestinal strictures.
- 10. Has feeding or decompression tubes and/or a gastric pacemaker.
- 11. Has had Botox pyloric injections within the prior 3 months.
- 12. Has had diabetic ketoacidosis (within the prior 4 weeks).
- 13. Currently taking Glucagon-like peptide-1 (GLP-1) agonists, e.g. exenatide, liraglutide, semaglutide or dulaglutide, or pramlintide.
- 14. Has severe psychiatric illness (including suicidal tendencies or ideation) or neurological illness.
- 15. History or suspicion of alcohol, barbiturate, amphetamine or narcotic abuse.

Version 3.0 34 of 85 20 April 2022

- 16. Use of narcotics/opioids, drugs used to treat gastroparesis within 3 days of the Screening GEBT test.
- 17. Anticipated concurrent use of a strong Cytochrome P450 (CYP) inhibiting or inducing drug (listed in Section 6.7.1) that would significantly alter the metabolism of PCS12852 and/or its metabolites during the course of the study (after Screening)
- 18. Fever (> 38°C), or chronic, persistent, or recurring infection(s) at Screening or baseline.
- 19. Clinically significant cardiac disease including but not limited to unstable angina, acute myocardial infarction within 6 months of baseline, and arrhythmia requiring therapy.

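### Tramadol and loperamide are allowed as rescue with no avoidance window before the Day 28 GEBT, although Section 6.7.1 bars opioids and GI-motility drugs (minor)

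*Combined protocol and SAP*

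**What the plan says.** Section 6.7.1 sets the prohibition by class: "The class of drugs prohibited in the study are those that affect GI motility, either positively or negatively". It gives the reason, which is that such drugs could confound the efficacy assessment. It then lists drugs by name: "Prohibited concomitant treatment includes cannabis, opioids, GLP-1 agonists", among others. It states no rescue exception and does not refer to Section 6.7.3.

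Section 6.7.3 opens with a general caution: "Use of medications that may impact efficacy evaluations is strongly discouraged at any time after Visit 1 in the study". It then allows one day per week of treatment "with an anti-emetic drug, but should avoid such treatment, if possible, on the day prior to and day of treatment visits", and asks for Medical Monitor contact if anti-emetic use is more frequent. A list of permitted rescue drugs follows, including "loperamide for diarrhea" and "Tramadol for pain". No dose, frequency or timing limit is attached to either. Use is documented: "The date and time of rescue medication administration as well as the name and dosage regimen of the rescue medication must be recorded".

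The only opioid washout tied to a breath test is exclusion 16 in Section 5.2: "Use of narcotics/opioids, drugs used to treat gastroparesis within 3 days of the Screening GEBT test". For the Day 28 test, the Synopsis and Sections 4.1 and 6.1 require an overnight fast and a fasting glucose of at most 275 mg/dL. They say nothing about rescue drugs.

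**The concern.** The primary endpoint is the change in GEBT AUC from the Screening test to the Day 28 test, so the two tests should be done under matching conditions. The plan matches fasting and glucose at both. For rescue drugs it does not: an opioid in the 3 days before the first test makes a patient ineligible, while tramadol shortly before the second test is only discouraged. Loperamide is in the same position at Day 28.

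That tramadol is an opioid and that loperamide slows gut motility is drug-class knowledge; the documents do not say so. If either drug slows gastric emptying, use near Day 28 in an active arm would shrink the observed difference, use on placebo would widen it, and use in both arms would add spread. With 8 patients per arm, one patient can be visible in the result.

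**Working it through.** **1. Which rule reaches which drug and which test**

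| Rule | Drugs covered | Test covered |
|---|---|---|
| 6.7.1 prohibition | Opioids, GI-motility drugs | Whole study, but 6.7.3 lists tramadol and loperamide as allowed |
| 6.7.3 day-before and day-of avoidance | Anti-emetics, if possible | Treatment visits, including Day 28 |
| 6.7.3 general discouragement | Any drug that may affect efficacy | After Visit 1; no window |
| 6.7.1 consultation with the Investigator | Any new drug or change | Throughout; no window |
| Exclusion 16, 3 days | Opioids, gastroparesis drugs | Screening GEBT only |
| Day 28 GEBT conditions | None (fast and glucose only) | Day 28 |

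Other opioids remain barred by 6.7.1. The exposure without a window at Day 28 is therefore rescue tramadol and loperamide only.

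**2. The plan's own power figure**

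Inputs from Section 9.3: difference 25, SD 15, 8 per arm, two-sided alpha 0.025, stated power 80%.

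Noncentrality = 25 / (15 × √(1/8 + 1/8)) = 25 / 7.5 = 3.33. With 14 degrees of freedom the critical value is 2.510 and power is 78.4%. With the three-arm pooled 21 degrees of freedom power is 81.3%. The stated 80% is reproduced.

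**3. Illustration of what rescue use could do**

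Model: active patients ~ N(25, 15), placebo ~ N(0, 15), 8 per arm; *k* patients in an arm shifted down by *s* units; pooled t-test at two-sided alpha 0.025; 400,000 simulated trials per case (Monte Carlo standard error below 0.001). The expected difference is 25 − *ks*/8 for use on active drug and 25 + *ks*/8 for use on placebo. The values of *k* and *s* are assumptions; the documents give neither.

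| Case | Expected difference | Power |
|---|---|---|
| No rescue use | 25 | 78% |
| 1 active, 5 units | 25 − 5/8 = 24.4 | 76% |
| 1 active, 12.5 units | 25 − 12.5/8 = 23.4 | 71% |
| 1 active, 25 units | 25 − 25/8 = 21.9 | 59% |
| 2 active, 25 units each | 25 − 50/8 = 18.75 | 39% |
| 1 placebo, 12.5 units | 25 + 12.5/8 = 26.6 | 82% |
| 1 placebo, 25 units | 25 + 25/8 = 28.1 | 83% |
| 1 in each arm, 12.5 units | 25 | 75% |
| 1 in each arm, 25 units | 25 | 66% |

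For scale, Section 9.3 gives an SD range of 10 to 35 from the prior study. The same t-test formula gives 99% power at SD 10 and 17% at SD 35, a wider spread than any case above.

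**4. Power of a sensitivity analysis that drops affected tests**

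With the full 25-unit effect and SD 15:
- 7 versus 8 patients: 25 / (15 × √(1/7 + 1/8)) = 3.22, 13 degrees of freedom, power 75%.
- 6 versus 8 patients: 25 / (15 × √(1/6 + 1/8)) = 3.09, 12 degrees of freedom, power 70%.

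All of these figures use the pairwise t-test behind Section 9.3, not the planned ANCOVA with Dunnett's test.

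**The case against.** The case for leaving the text alone has several parts.

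- *The sections do not truly conflict.* A named rescue list after a general prohibition is normally read as an exception, and Section 6.7.2 sends doubts about a specific drug to the Medical Monitor. This stands. A reader might infer a flat contradiction, but only a cross-reference is missing.
- *Use near Day 28 is already controlled.* Discouragement applies at any time after Visit 1, and patients consult the Investigator before any new drug. This stands in part. The plan does not invite such use, but neither control sets a window, and an Investigator who is consulted would find both drugs listed as allowed. For anti-emetics the plan adds a visit-specific rule despite the same general caution.
- *Use may be rare.* Section 2.2 puts diarrhea among the most frequent events, which makes loperamide use conceivable. Section 4.3 says that Phase 1 adverse events were generally mild and resolved without treatment. That covers diarrhea as well, so it weakens the case for loperamide as much as for tramadol. This stands.
- *No effect on the test is documented.* Nothing in the protocol says that either drug changes the GEBT. This stands, and it rules out reading the power table as an estimate.
- *Rescue may belong to the treatment regimen.* The primary analysis takes all randomized patients, and no estimand without rescue is stated. If rescue counts as part of the regimen, a difference that includes it is the target, not bias. This stands against calling 26.6 or 28.1 an overstatement outright.
- *The SAP can handle it.* Section 9 defers detail to a SAP finalized before database lock, and rescue dates and times are recorded. That covers the analysis, but a SAP cannot set a rule for patients before the test.

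**Conclusion.** The gap holds on the text: no stated window protects the Day 28 GEBT from rescue tramadol or loperamide, although the protocol treats motility drugs as confounders and protects the Screening test from opioids. Confidence in that reading is high. Confidence in any consequence is not: the documents give no rescue rate, no timing and no effect of these drugs on the test.

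A reader might infer that the primary result is biased in a known direction, or that power would fall to 59% or 39%. The documents support neither. Those two figures need one or two active-arm patients to lose the whole assumed 25-unit effect; a 5-unit loss in one patient costs about 2 points, and use on placebo moves the difference the other way. Severity is minor: a cheap improvement to a 24-patient Phase 2a plan.

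**What to change.** - **Section 6.7.1:** cross-reference the 6.7.3 rescue drugs as the only exceptions to the prohibition.
- **Section 6.7.3:** add that, unless medically necessary, tramadol is avoided for 3 days before the Day 28 GEBT (the length used in exclusion 16), and loperamide on the day before and the day of it (the rule used for anti-emetics). Count back from the actual test, because a high fasting glucose moves it to the next day. If the drug is needed, give it and record it; the one-day Visit 6 window is too short to wait out 3 days.
- **Analysis:** keep the full analysis set ANCOVA as primary and report rescue use by arm. Optionally, pre-specify in the SAP one sensitivity ANCOVA that excludes Day 28 GEBTs taken inside those windows. It should state that it can exclude patients whose rescue was medically necessary, that it conditions on post-randomization use, and that its power is lower (about 75% or 70% with 1 or 2 of 8 removed from one arm). It cannot replace the primary analysis.

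The cost is two wording changes, slightly tighter rescue limits before Day 28, and at most one extra analysis on data already collected.

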7.1.1 Stopping Criteria

PCS12852 is a highly selective 5-hydroxytryptamine receptor 4 (5-HT₄ receptor) agonist. As such, the stopping rules focus on the known cardiac safety concerns identified for the drug class of 5-HT₄ receptor agonists. The overall study will be stopped if \geq 2 patients develop the same Grade 3 CTCAE cardiac event or 1 patient develops a CTCAE \geq Grade 4 cardiac event.

For cardiac adverse events classified as $CTCAE \ge Grade 3$, if the same cardiac safety concern is seen on two separate ECGs, the patient should be withdrawn from the study and will be referred to a cardiologist for the appropriate treatment.

Version 3.0 43 of 85 20 April 2022

7.2 Loss to Follow-Up/Early Discontinuation from Study Drug

A patient will be considered lost to follow-up if they repeatedly fail to return for scheduled visits and are unable to be contacted by the study site.

The following actions must be taken if a patient fails to return to the clinic for a required study visit:

- The site must attempt to contact the patient and reschedule the missed visit as soon as possible (and within the visit window, where one is defined), counsel the patient on the importance of maintaining the assigned visit schedule, and ascertain whether the patient wishes to and/or should continue in the study.
- In cases in which the patient is deemed lost to follow-up, the Investigator or designee must make every effort to regain contact with the patient (where possible, three telephone calls and, if necessary, a certified letter to the patient's last known mailing address or local equivalent methods). These contact attempts should be documented in the patient's medical record/eCRF.
- Should the patient continue to be unreachable, he/she will be considered to have withdrawn from the study.

If a patient discontinues study drug prior to study termination, the patient will be asked to return to the clinic for an Early Termination visit. This visit will include all the study procedures of the Day 35/Visit 8 clinic visit. The Day 35 study procedures and their timing are summarized in the SoA (Table 1).

8 Study Assessments and Procedures

Study procedures and their timing are summarized in the SoA (Table 1).

Immediate safety concerns should be discussed with the Medical Monitor immediately upon occurrence or awareness to determine if the patient should continue or discontinue study treatment.

Adherence to the study design requirements, including those specified in the SoA (Table 1), is essential and required for study conduct.

All screening evaluations must be completed and reviewed to confirm that potential patients meet all eligibility criteria. The Investigator should maintain a screening log to record details of all patients screened and to confirm eligibility or record reasons for screening failure, as applicable.

Version 3.0 44 of 85 20 April 2022

Repeat or unscheduled samples may be taken for safety reasons or for technical issues with the samples.

Patient Identification Card

All patients will be given a patient identification card identifying them as patients in a research study. The card will contain study site contact information (including direct telephone numbers) to be used in the event of an emergency. The Investigator or qualified designee will provide the patient with a patient identification card immediately after the patient provides written informed consent. At the time of treatment allocation/randomization, site personnel will add the treatment/randomization number to the patient identification card.

Medical History

A medical history will be obtained by the Investigator or qualified designee. The medical history will collect all active conditions and any condition diagnosed within the prior 5 years that the Investigator considers to be clinically relevant. Details regarding the disease for which the patient has enrolled in this study will be recorded separately and not listed as medical history.

